4.5.2 Medical History and Demographic Data

Medical history, including clinically significant diseases and surgeries within 5 years prior to initiation of study treatment, cancer history (including prior cancer therapies, surgeries, and procedures), and use of alcohol, will be recorded at baseline. In addition, all medications (e.g., prescription drugs, over-the-counter drugs, herbal or homeopathic remedies, nutritional supplements) used by the patient within 7 days prior to initiation of study treatment will be recorded. At the time of each follow-up physical examination, an interval medical history should be obtained and any changes in medications and allergies should be recorded.

Demographic data will include age, sex, and self-reported race/ethnicity (where permissible).

4.5.3 Physical Examinations

A complete physical examination, performed at screening and other specified visits, should include an evaluation of the head, eyes, ears, nose, and throat (HEENT), neck, and the cardiovascular, dermatological, musculoskeletal, respiratory, gastrointestinal, genitourinary, and neurological systems. HEENT examination should include visual inspection and/or palpation of the oral cavity and oropharynx, and palpation of the draining lymph nodes of the neck. Any abnormality identified at baseline should be recorded on the General Medical History and Baseline Conditions eCRF.

Limited, symptom-directed physical examinations, consisting of an evaluation of the oral cavity, oropharynx, head and neck (including lymph nodes), lungs, heart, abdomen, and skin, should be performed at specified post-baseline visits and as clinically indicated. Patients should be asked specifically about skin and vision changes as part of each physical examination. Changes from baseline abnormalities should be recorded at each subsequent physical examination. New or worsened clinically significant abnormalities should be recorded as adverse events on the Adverse Event eCRF.

Patients should be asked specifically about skin and vision changes as part of each physical examination.

As part of tumor assessment, physical examinations should also include the evaluation of the presence and degree of enlarged lymph nodes, hepatomegaly, and splenomegaly.

4.5.4 Vital Signs

Vital signs include measurements of heart rate, respiratory rate, and systolic and diastolic blood pressures while the patient is in a seated position, as well as oral or tympanic temperature. Blood pressure and heart rate measurements will be recorded after a 5-minute rest while the patient is in a seated position. Resting oxygen saturation will be measured during screening.

Vital signs should be measured within 60 minutes prior to each atezolizumab infusion and, if clinically indicated, during or after the infusion. In addition, vital signs should be measured at other specified timepoints as outlined in the schedule of activities (see [Appendix 1](#)).

4.5.5 Tumor and Response Evaluations

All measurable and non-measurable lesions must be documented at screening (within 28 days prior to initiation of study treatment). Previously irradiated lesions should not be selected as measurable (target) lesions. Evaluation of tumor response conforming to RECIST v1.1 must then be documented every 8 weeks (\pm 1 week) from the date of first study drug administration (Run-In Day 1) through 24 months (e.g., Weeks 8, 16, 24, 32, etc.) and then every 12 weeks (\pm 1 week) thereafter, until investigator-determined disease progression (according to RECIST v1.1, that is confirmed 4–8 weeks after initial documentation of progression) or death, whichever occurs first. Thus, tumor assessments are to continue according to schedule in patients who discontinue treatment for reasons other than disease progression. At the investigator's discretion, tumor assessments may be repeated at any time if disease progression is suspected.

Tumor assessments must be performed independently of changes to the study treatment administration schedule (i.e., when treatment is withheld). If a tumor assessment has to be performed early or late, subsequent assessments should be conducted according to the original schedule based on the date of first study treatment administration (Run-In Day 1).

Tumor assessments will include contrast-enhanced CT or MRI scans of the chest, abdomen, and pelvis. Imaging of the neck should be included if clinically indicated. In the event a positron emission tomography (PET)/CT scanner is used for tumor assessments, the CT portion of the PET/CT must meet criteria for diagnostic quality. A CT or MRI scan of the head must be performed at screening to assess CNS metastasis. An MRI scan of the brain is required to confirm or refute the diagnosis of CNS metastases at baseline in the event of an equivocal scan. Patients with untreated or actively progressing CNS metastases are not eligible for the study (see [Section 4.1.2](#)). Stable brain metastases (as defined in [Section 4.1.2](#)) must be evaluated at each tumor assessment with the same radiographic procedure as the baseline study.

Patients without brain metastases do not need brain scans for tumor assessment unless clinically warranted. Clinical disease assessments by physical examination should be performed for patients with palpable/superficial lesions. Tumor measurements for each patient should be made by the same investigator or radiologist, if feasible, using the same assessment technique or procedure throughout the study.

Tumor response and progression will be evaluated according to RECIST v1.1 (see [Appendix 4](#)) and [REDACTED]. Objective response (complete or partial response) must be confirmed by repeat assessments ≥ 4 weeks after initial documentation. In the case of stable disease, tumor measurements must meet criteria for stable disease ≥ 6 weeks after initiation of study treatment.

4.5.6 Study-Specific Safety Monitoring Assessments

4.5.6.1 Monitoring for New Primary Neoplasms

All new primary neoplasms (benign or malignant), including new primary melanoma, will be reported until 6 months after the final dose of vemurafenib. Any new primary neoplasm other than cuSCC should be reported as a serious adverse event.

Dermatologic Evaluation

Evaluations of the skin by a dermatologist, or qualified equivalent medical specialist, will be performed at specified timepoints during the study. An unscheduled dermatology examination may be performed during treatment for investigation of any new skin lesions that are suspected of being cuSCC or another new primary cutaneous neoplasm.

The dermatologic evaluation should include the following:

- Complete history of prior dermatologic medications and cuSCC risk factors (i.e., radiation therapy, sun exposure, immunosuppression, prior cuSCC, use of tanning beds, precursor lesions, and phototherapy for psoriasis)
- Skin examination for cuSCC, BCC, actinic keratosis, keratoacanthoma (KA), and/or second primary melanoma
- Appropriate mapping of any suspicious lesions that may represent cuSCC, BCC, actinic keratosis, KA, or second primary melanoma
- Biopsy and/or excision of any suspicious lesions and submission of specimen blocks or sections for pathologic examination by the local laboratory according to local standard of care
- Treatment of identified skin neoplasms or conditions per local standard of care

Head and Neck Evaluation

To monitor for the occurrence of SCC in the upper aerodigestive tract, a head and neck examination will be performed by the investigator or his or her designee at screening, specified timepoints during the study, and as clinically indicated (e.g., if any new head and neck lesions are suspected of being non-cuSCC). Assessments will include (at a

minimum) examination of the HEENT and neck, visual inspection of the oral mucosa, and lymph node palpation.

Any suspicious lesions that are identified will be evaluated, biopsied, or excised if indicated and followed up according to local standard of care.

Lung Examination

Patients will undergo CT or MRI scans of the chest to monitor for the occurrence of lung SCC. The chest CT or MRI scans performed as part of regularly scheduled tumor assessments may be used for lung SCC surveillance.

Anal Examination

To monitor for anal SCC, visual inspection and digital examination of the anus and anal canal will be performed by the investigator or his or her designee at specified timepoints during the study and as clinically indicated. Colonoscopy, sigmoidoscopy, or anoscopy is not required but may be performed if clinically indicated. Any suspicious lesions that are identified will need to be evaluated and biopsied if indicated according to local standard of care.

Gynecological Examination

To monitor for cervical carcinoma, all female patients will undergo a pelvic examination, including visual inspection of the uterine cervix and Papanicolaou (Pap) smear, at specified timepoints during the study and as clinically indicated.

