5.1.5.2 Dose Modifications during the Triplet Treatment Period

There will be no dose modifications for atezolizumab in this study.

The dose of cobimetinib can be reduced by 20 mg QD (one dose level) decrements up to two times for management of drug-related toxicities (i.e., from 60 to 40 mg and then from 40 to 20 mg), except during run-in period when only one dose reduction is allowed. If further dose reduction is indicated after two dose reductions, the patient must

discontinue cobimetinib but may continue treatment with atezolizumab and/or vemurafenib at the investigator's discretion. The dose of cobimetinib may be escalated by a maximum of one dose level (20 mg) from 20 mg QD to 40 mg QD at the investigator's discretion in patients who have previously undergone dose reduction, provided there are no safety concerns. Dose escalation from 40 mg QD to 60 mg QD is not permitted.

The dose of vemurafenib can be reduced by 240 mg/matching placebo BID (one dose level) decrements up to two times for management of drug-related toxicities (i.e., from 960 mg/matching placebo BID to 720 mg/matching placebo BID and then from 720 mg/matching placebo BID to 480 mg/matching placebo BID), except during the run-in period, when only one dose reduction is allowed. If further dose reduction is indicated after two dose reductions, the patient must discontinue vemurafenib but may continue treatment with atezolizumab and/or cobimetinib at the investigator's discretion. The dose of vemurafenib may be escalated by a maximum of one dose level (240 mg/matching placebo dose BID) from 480 mg/matching placebo dose BID to 720 mg/matching placebo BID at the investigator's discretion in patients who have previously undergone dose reduction, provided there are no safety concerns. Dose escalation from 720 mg/matching placebo BID to 960 mg/matching placebo BID is not permitted.

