5.3.1 Adverse Event Reporting Period

Investigators will seek information on adverse events at each patient contact. All adverse events, whether reported by the patient or noted by study personnel, will be recorded in the patient's medical record and on the Adverse Event eCRF.

After informed consent has been obtained **but prior to initiation of study treatment**, only serious adverse events caused by a protocol-mandated intervention (e.g., invasive procedures such as biopsies, discontinuation of medications) should be reported (see Section 5.4.2 for instructions for reporting serious adverse events).

After initiation of study treatment, adverse events will be reported as follows:

- All adverse events will be reported until 30 days after the final dose of study treatment or until initiation of subsequent anti-cancer therapy, whichever occurs first
- Serious adverse events and [REDACTED] will continue to be reported until 90 days after the final dose of study treatment or until initiation of subsequent anti-cancer therapy, whichever occurs first.
- All new primary neoplasms (benign or malignant), including new primary melanoma, will be reported until 6 months after the final dose of vemurafenib. Any new primary malignant neoplasm other than cutaneous squamous cell carcinoma should be reported as a serious adverse event.

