Appendix 1 Schedule of Activities

Day	Screening ^a		Run-In Period (Days 1–28) ^b			Triple Combination Period ^c								Treatment Discon. ^d	Follow-Up					
	-28 to -1	-14 to -1	1	15	21	1	8	15	22 ^e	1	8	15	22	1	15	28	2 mos	3 mos	4 mos	6 mos
Visit window (days) ^f	x ^f			±3	±3	±3	±3	±3	±3	±3	±3	±3	±3	±3	±3	±7	±7	±7	±7	±14
Informed consent	x ^g																			
Randomization			x ⁱ																	
BRAF ^{V600} mutation status	x ^a																			
Demographic data ^j	x																			
Medical history ^k	x																			
EORTC QLQ-C30 ^l			x		x	x		x		x	x	x	x	x	x ^m		x ^m	x ^m		
Height and weight	x																			
ECOG performance status	x					x			x		x		x		x					
Complete physical examination ⁿ	x		x ^o												x					
Limited physical examination ⁿ					x			x		x		x		x		x	x	x	x	
Head and neck examination ^p	x										x ^p		x ^p		x ^p		x ^p	x ^p	x ^p	
Anal and gynecological examinations ^q	x											x		x				x ^q		
Dermatologic examination ^r	x				x					x ^r		x ^r		x ^r				x ^r		
Ophthalmologic examination ^s	x				x					x ^s		x ^s		x ^s						

Appendix 1
Schedule of Activities (cont.)

Day	Screening ^a		Run-In Period (Days 1–28) ^b			Triple Combination Period ^c								Treatment Discon. ^d	Follow-Up					
						Cycle 1				Cycle 2										
	-28 to -1	-14 to -1	1	15	21	1	8	15	22 ^e	1	8	15	22	1	15	28	2 mos	3 mos	4 mos	6 mos
Visit window (days) ^f	x ^f			±3	±3	±3	±3	±3	±3	±3	±3	±3	±3	±3	±3	±7	±7	±7	±7	±14
Cutaneous SCC or suspicious neoplasms ^t			Any new primary neoplasms that develop from the start of study treatment through 6 months following vemurafenib discontinuation ^s																	
Vital signs ^u		x ^{u, v}		x		x	x	x	x	x	x	x	x	x	x	x				
Hematology ^w		x	x ^o			x				x					x		x			
Chemistry ^x		x	x ^o	x		x	x	x	x	x	x	x	x	x	x	x	x			
Thyroid-function tests ^y	x				x				x					x ^y		x				
Viral serology ^z	x																			
Pregnancy test ^{aa}		x ^{v, aa}			x ^{aa}				x ^{aa}			x ^{aa}		x ^{aa}						
Fasting blood glucose and lipids ^{bb}	x																			
INR and aPTT	x																			
12-Lead ECG ^{cc}		x		x			x			x			x ^{cc}		x					
Radiologic tumor assessment ^{dd}	x ^{ee}									Last week of Cycle 1 and every 8 or 12 weeks thereafter ^{ee}										
Additional chest CT or MRI scan																				x ^{ff}
Brain CT or MRI scan	x ^{gg}		As clinically indicated ^f																	

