^p To monitor for the occurrence of SCC in the upper aerodigestive tract, a head and neck examination will be performed at screening, Day 1 of Cycle 3 and every three cycles thereafter during treatment (i.e., Day 1 of Cycles 6, 9, 12, etc.) (\pm 1 week), at the treatment discontinuation visit (unless performed within the previous 12 weeks), at 3 and 6 months (\pm 2 weeks) after the final dose of study treatment, and as clinically indicated (e.g., if any new head and neck lesions are suspected of being non-cuSCC). Assessments will include (at a minimum) examination of the HEENT and neck, visual inspection of the oral mucosa, and lymph node palpation.

^q To monitor for anal SCC, visual inspection and digital examination of the anus and anal canal will be performed at screening, at the treatment discontinuation visit, 6 months (\pm 2 weeks) after the final dose of vemurafenib, and as clinically indicated. Colonoscopy, sigmoidoscopy, or anoscopy is not required but may be performed if clinically indicated. To monitor for cervical carcinoma, all female patients will undergo a pelvic examination, including visual inspection of the uterine cervix and Papanicolaou (Pap) smear, at screening, at the treatment discontinuation visit, 6 months (\pm 2 weeks) after the final dose of vemurafenib, and as clinically indicated. Pelvic examinations performed within 12 months prior to screening need not be repeated if found to be normal.

Appendix 1

Schedule of Activities (cont.)

- r A complete dermatologic evaluation (as described in Section 4.5.6.1) should be performed at screening, on Day 1 of Cycle 1 and every three cycles thereafter during treatment (i.e., Day 1 of Cycles 4, 7, 10, etc.) (\pm 1 week), at the treatment discontinuation visit (unless performed within the previous 12 weeks), 6 months (\pm 2 weeks) after the final dose of study treatment, and as clinically indicated.
- s Ophthalmologic examinations (as described in Section 4.5.6.2) should be performed at screening; on Day 1 of Cycle 1 (\pm 1 week), Cycles 4, 7, 10, 14, 18, 22, and every six cycles thereafter (i.e., Cycles 28, 34, 40, etc.) (\pm 2 weeks for each); at the treatment discontinuation visit (unless examination performed within the previous 12 weeks showed no clinically significant findings or changes since the prior examination), and as clinically indicated.

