Appendix 1 Schedule of Activities (cont.)

[figure not shown]
- ^{ff} To monitor for SCC, an additional chest CT or MRI scan must be performed 6 months (\pm 2 weeks) after the final dose of study treatment.
- ^{gg} Patients must have a screening brain CT or MRI scan to assess for brain metastasis. Stable brain metastases (as defined in Section 4.1.2) must be evaluated at each tumor assessment with the same radiographic procedure as the baseline study. Patients without brain metastases do not need brain scans for tumor assessment unless clinically warranted.
- ^{hh} Evaluation of left ventricular function, either by ECHO or MUGA scan, will be performed at screening, on Day 1 of Cycle 1 (\pm 1 week), and on Day 1 of every three treatment cycles thereafter starting at Cycle 4 (\pm 2 weeks for each), at the treatment discontinuation visit (unless evaluation performed within the previous 12 weeks showed no clinically significant findings or changes from baseline), and as clinically indicated. All patients who restart treatment with a reduced dose of cobimetinib because of a decrease in LVEF should have LVEF measurements taken after approximately 2, 4, 10, and 16 weeks (or as clinically indicated) and then resume monitoring LVEF every 12 weeks (three cycles). Any patient who develops clinical signs or symptoms suspicious of cardiac failure should undergo an LVEF assessment. For patients (asymptomatic and symptomatic) who discontinue cobimetinib, LVEF assessments should continue 6 weeks post-treatment or as clinically indicated until the LVEF recovers to LLN or 50% and or symptoms. These evaluations are not required for patients who have permanently discontinued cobimetinib and who do not have reduced left ventricular function.

- ⁱⁱ [REDACTED]
- ^{jj} Includes any medication (e.g., prescription drugs, over-the-counter drugs, vaccines, herbal or homeopathic remedies, nutritional supplements) used by a patient in addition to protocol-mandated study treatment from 7 days prior to signing of the Informed Consent Form through 30 days after the final dose of study treatment.

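### New primary neoplasm reporting is counted from the last vemurafenib dose, but the final dermatologic, head-and-neck and chest examinations are counted from the last dose of any study drug, so some of what they find need not be reported

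*Protocol*

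**What the plan says.** **Reporting limit.** Protocol Section 4.5.6.1: "All new primary neoplasms (benign or malignant), including new primary melanoma, will be reported until 6 months after the final dose of vemurafenib". Sections 5.1.3.1, 5.1.3.2, 5.3.1 and 5.4.2.2 and Appendix 1 footnotes t and kk use the same limit. The neoplasm row of Appendix 1 words the scope differently: "Any new primary neoplasms that develop from the start of study treatment through 6 months following vemurafenib discontinuation".

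**Examinations.** Appendix 1 footnote p sets head-and-neck examinations at 3 and 6 months, and footnote r sets a dermatologic examination at 6 months. Each has a 2-week tolerance either way and is timed "after the final dose of study treatment, and as clinically indicated". Footnote ff adds: "To monitor for SCC, an additional chest CT or MRI scan must be performed 6 months", with the same tolerance and the same starting point. Footnote q counts the anal and gynecological examinations from the last vemurafenib dose instead.

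**Order of stopping.** Section 4.3 names three investigational products. Section 5.1.5.2 says that, when more than two dose reductions would be needed, "the patient must discontinue vemurafenib but may continue treatment with atezolizumab and/or cobimetinib". Table 3 has other routes to the same state, in the QTcF rows and at a third hepatic episode.

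**Other windows.** Section 5.3.1: "All adverse events will be reported until 30 days after the final dose of study treatment". Serious events run to 90 days. Both limits come sooner if subsequent anti-cancer therapy starts. After that, Section 5.6 asks only for deaths and for serious events believed related to study treatment. Cutaneous SCC is the stated exception to automatic serious status.

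**The concern.** The protocol requires specialist examinations and a scan in order to find second cancers, but the duty to report those cancers runs on a different clock. The two clocks agree only when vemurafenib is the last drug taken, and even then only for the first half of the visit tolerance.

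Cutaneous SCC is an identified vemurafenib risk (Section 5.1.3) and a named target of the dermatologic examination (Section 4.5.6.1). SAP Section 4.5.2 summarizes all adverse events from the first dose onward and sets no end date of its own. The collection rule therefore decides what is counted, and an event that was never required to be reported cannot appear in the tables. The direction of any error is under-counting.

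**Working it through.** The plan gives no figure to reproduce, so the check is date arithmetic.

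**Inputs.** Let g be the days from the last vemurafenib dose to the last dose of any study drug. Take 6 months as 365.25/2 = 182.6 days (an assumption). The tolerance is 14 days (Appendix 1), and the other limits are 30 and 90 days (Section 5.3.1). Days are counted from the last vemurafenib dose:

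- neoplasm reporting closes: 182.6
- adverse event reporting closes: g + 30
- serious event reporting closes: g + 90
- examination window: g + 182.6 ± 14, that is, g + 168.6 to g + 196.6

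**Against the 30- and 90-day limits.** Since 168.6 exceeds both 30 and 90, the 6-month examinations fall after both limits for every g.

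**Against the neoplasm limit.** The window lies wholly after closure when g + 168.6 > 182.6, that is, when g > 14. For smaller g, the share after closure is (g + 14)/28.

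| g (days) | Examination window (days after vemurafenib) | Neoplasm reporting closes | Share of window after closure |
|---|---|---|---|
| 0 | 169–197 | 183 | 0.50 |
| 14 | 183–211 | 183 | 1.00 |
| 28 | 197–225 | 183 | 1.00 |
| 84 | 253–281 | 183 | 1.00 |
| 168 | 337–365 | 183 | 1.00 |

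The values of g are illustrative, because the documents give no distribution for it and no upper limit.

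**Uncovered time before the examination.** For a non-serious event the last limit to close is the larger of 182.6 and g + 30.

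- g = 28: max(182.6, 58) = 182.6, so the examination comes 14 to 42 days later.
- g = 84: max(182.6, 114) = 182.6, so 70 to 98 days later.
- g = 168: max(182.6, 198) = 198, so 336.6 − 198 = 139 to 364.6 − 198 = 167 days later. For a serious event the limit is 168 + 90 = 258, so 79 to 107 days later.

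**Example in months.** Vemurafenib stops at month 3 and the other drugs at month 12. Neoplasm reporting closes at 3 + 6 = 9, adverse events at 12 + 1 = 13 and serious events at 12 + 3 = 15. The examinations fall at 12 + 6 = 18. Because adverse event collection is still open from month 9 to month 13, the uncovered stretch is months 13–18 for cutaneous SCC and months 15–18 for neoplasms that count as serious.

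**What Section 5.6 leaves out.**

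- Malignant neoplasm other than cutaneous SCC, believed related: serious, so it has a route with no time limit.
- The same, judged unrelated: no route.
- Cutaneous SCC: no route unless it is serious on other grounds and believed related.
- Benign neoplasm: unclear. Section 4.5.6.1 and footnote t make every new primary neoplasm except cutaneous SCC serious, whereas Section 5.3.1 does so only for malignant ones.

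**The case against.** The strongest case is that this is visit tolerance plus a deliberate choice to follow vemurafenib risks on a vemurafenib clock. Four points support it.

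- **Scope by onset.** The neoplasm row of Appendix 1 counts lesions that develop within the limit. A lesion first seen a few days late may have arisen in time. This stands. A reader might infer that half of the final findings are lost when vemurafenib is the last drug, but the 0.50 is a share of the permitted visit window, not of findings.
- **Collection while other drugs continue.** Adverse events and serious events are still collected, and on-treatment skin examinations recur every three cycles. This stands and confines the gap to the time after the last study drug. Section 5.1.3.1 also describes cutaneous SCC as usually an early event.
- **Late routes.** Section 5.6 has no time limit, and Table 5 treats an event as related unless stated criteria are met. A reader might infer that these findings lie outside every reporting route. For related malignancies other than cutaneous SCC they do not.
- **The 6-month visit.** Appendix 1 marks adverse events there, and footnote n sends new abnormalities on physical examination to the Adverse Event form. This helps only in part: the adverse event mark carries footnote kk, which repeats the vemurafenib limit, and footnote n does not reach a chest scan.

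A reader might also infer a bias between arms, since vemurafenib doses differ and only one arm receives atezolizumab. The documents give neither vemurafenib discontinuation nor g by arm, Table 3 allows both arms the same number of tablet reductions, and the legible SAP text names no neoplasm comparison.

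**Conclusion.** The mismatch is in the current text and should be corrected. If vemurafenib stops more than 14 days before the last study drug, the final dermatologic and head-and-neck examinations and the SCC chest scan always come after neoplasm reporting has closed and after the 30- and 90-day limits. If vemurafenib is last, the overrun is at most 14 days. These results rest only on the stated dates and on both starting points being meant literally.

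The findings not required to be reported are mainly late cutaneous SCC and late neoplasms judged unrelated. Their number cannot be estimated from the documents, and a difference by arm is possible but not shown. No efficacy analysis is touched. The issue is the completeness of one safety count.

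**What to change.** In Protocol Sections 4.5.6.1, 5.3.1 and 5.4.2.2 and in Appendix 1 (neoplasm row, footnotes t and kk), require new primary neoplasms to be reported until the later of:

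- (a) 6 months after the last vemurafenib dose; and
- (b) 6 months plus the 2-week visit tolerance after the last dose of study treatment.

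Add that any neoplasm found at a protocol-required 6-month examination is reportable even if pathology returns later. Carry the same limit into Sections 5.1.3.1 and 5.1.3.2, which restate it. Since vemurafenib is itself study treatment, (b) will govern in practice; keeping (a) makes plain that the present window is never shortened.

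A calendar limit is safer than closing reporting once the last examination is done. An examination done early in its tolerance would then shorten the present window, and a missed one would leave no end date. Use the same edit to settle whether benign neoplasms count as serious.

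Counting the examinations from vemurafenib, as footnote q does, would also reconcile the text. That would change surveillance, however, and the documents do not show which starting point was intended. The change proposed here affects data collection only.

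Cost: one sentence in each place, a few more neoplasm reports, and a longer collection period in patients who stop vemurafenib early. No visits or examinations are added.
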